Aim 2: To compare the effects of the interventions on volume and pattern of sedentary behavior and physical activity and determine if these factors predict weight regain during the 9-month follow-up phase.

Hypothesis: WL+EX+SitLess will have higher total physical activity energy expenditure, less sedentary behavior, more breaks in sedentary behavior, and more minutes of light and moderate-vigorous activity averaged across follow-up than either WL+EX or WL+SitLess.

Hypothesis: Irrespective of treatment arm, greater activity energy expenditure and fewer minutes of sedentary behavior after the WL phase will be predictive of less weight regain during follow-up.

Aim 3: To evaluate treatment effects on clinical outcomes (body composition, functional fitness, cardiometabolic risk, fatigue, appetite) and social cognitive measures.

Hypothesis: WL+EX+SitLess will improve these tertiary outcomes more than either WL+EX or WL+SitLess.

Methods and Measures

Study Overview: We will use a 3-group design in up to 189 older (65-85 years), obese (BMI=30-45 kg/m²), sedentary men and women, all of whom will undergo a 9-month WL intervention (6-mo intensive phase and 3-mo reduced contact phase), followed by a 9-month self-managed follow-up phase with minimal contact, to test our overall hypothesis that intervening on SB will enhance long-term WL in this age group. **The diet element of the intervention is identical across groups, but groups differ by activity intervention:** 1) structured, moderate-intensity, aerobic exercise (WL+EX); 2) intervening on SB throughout the day (WL+SitLess); or 3) (WL+EX+SitLess).

Recruitment of study participants: Our recruitment goals include: 50% women and 20% minority. We will recruit these individuals using community-based recruitment strategies, including newspaper and radio advertisements, and mass mailings. **Specific inclusion/exclusion criteria (see table) are in place to eliminate those that may be adversely affected by the interventions or that are not able to comply with the interventions.** To reduce adverse effects of dietary WL we exclude individuals that are non-obese, those with recent WL, those who have low bone density, are being treated for osteoporosis, or taking medication that may affect bone density, and/or those who have deficient levels of vitamin D (25 hydroxyvitamin D level < 20 ng/mL) who are not taking a calcium/vitamin D supplement. We also exclude anyone who cannot walk unassisted.

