refraining from food, beverages (with the exception of water), alcohol and caffeine. Before any data collection, participants provide written informed consent and complete a HIPAA authorization form in accordance with our IRB policy. At this visit, weight and height will be measured to calculate BMI. Individuals who meet the BMI criteria will undergo a medical history and a cognitive test (MoCA). The medical history (including blood pressure, review of medications, and a fasting blood draw for metabolic panel, vitamin D level, and blood cell count) will exclude those with recent history of coronary heart disease, cancer, liver or renal disease, severe pulmonary disease, gross physical impairment, uncontrolled hypertension, or any contraindications to exercise. The fasting blood profile will exclude those with uncontrolled diabetes,⁶⁹ anemia, or liver, renal, or hematological dysfunction. Individuals with abnormal results at screening will be referred to their physicians. Prior to randomization, eligible participants will be asked if they would like to participate in an MRI ancillary study. This is visit 2.1 listed in the table on page 7. Refusal to participate in the ancillary study will not exclude them from the main (parent) study. See Appendix A for details of the MRI ancillary study. Eligible participants will be randomized to treatment using a web-based randomization scheme developed by the biostatistician, stratified by sex with random block sizes.

Study Interventions

Weight Loss intervention: 9-mo WL phase—All participants will undergo a dietary WL intervention designed to elicit behavioral changes leading to decreased caloric intake sufficient to yield a ~10% loss of initial body mass. The WL intervention includes nutrition education, state-of-the-art behavioral methods for promoting WL, and strategies that optimize self-regulation.^{8, 70, 71} During the intensive phase of WL (months 1-6), participants will meet in weekly group sessions delivered by either the RD or staff trained on specific elements of the intervention with individual sessions possible on an as needed basis. These group meetings will transition to bimonthly group meetings during months 7-9 and to monthly follow-up phone/email contact during the follow-up phase (months 10-18).

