The Fitbit and website are used to induce behavior change over the course of the intervention; participants begin wearing the Fitbit daily for the first 9 months and then wear time is tailored to each individual for the remainder of the study, however, we ask that all participants use the devices at least 2 days each week as described above.

The SitLess intervention counseling sessions occur in conjunction with the WL sessions and follow the same contact schedule to achieve treatment goals. Participants meet weekly during the first 6 months and bimonthly during months 7-9. These sessions will focus on: (1) reviewing data from the activity monitors, (2) reinforcement for observed changes in behavior, and (3) motivational interviewing and problem solving to increase commitment to change and assist with overcoming barriers.⁷³ The goal is to build commitment to the use of the devices and to link the feedback to improvements in personally-valued outcomes in their daily lives.

9-mo Follow-up phase—During this phase, participants will receive a monthly phone call or email contact for the purpose of emphasizing adherence to the SitLess goals and the Fitbit activity tracking and associated website.

Aerobic exercise intervention: 9-mo WL phase—Participants in the WL+EX and WL+EX+SitLess treatment arms will be asked to perform structured aerobic exercise (mostly treadmill walking) of moderate-intensity for 4-5 days/week, progressing to a duration of 200

min/week. Participants will attend center-based sessions for at least 3 days/week during the first intensive 6-month phase and at least one day/week during the second 3-month transition phase (months 7-9), with recording of home-based exercise for the other 2-4 days/week. The rationale for, background education on exercise training, and monitoring of study progress occurs in conjunction with the WL sessions in a manner consistent with the SitLess intervention. The level of exercise is based on current public health recommendations from the American Heart Association and American College of Sports Medicine (ACSM) for optimizing cardiovascular fitness in older adults,⁷⁴ and the ACSM recommendation for appropriate physical activity strategies for WL.⁷⁵

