Participants in all three groups will receive a Fitbit activity monitor, prior to the start of intervention, to assist with self-monitoring of their prescribed activity (e.g., aerobic exercise and/or decreased daily SB). As stated above, they will be encouraged to wear the Fitbit daily during the 9-month WL phase, and to wear it at least twice/week during the 9-month follow-up phase. If the monitor is lost, stolen or damaged they will be provided with a replacement. If a participant withdraws from the study, they will be asked to return the Fitbit. After completion of the last study visit, participants will be allowed to keep the Fitbit.

In addition, the study interventions require the use of a smartphone to upload data from the Fitbit and to access the study website to receive encouragement and motivation. If a participant does not own a smartphone or their smartphone is not compatible with our applications, the study will provide them with a smartphone and a phone/data plan for the length of their participation in the

study. Participants will be expected to keep the phone with them daily and to take care not to lose or damage it. Participants will be instructed that the phone is for study use only. If the phone is lost, stolen or damaged they will be provided with a replacement. If a participant withdraws from the study, they will be asked to return the smartphone and it will be deactivated immediately. After completion of the last study visit (V8), participants will return the smartphones and they will be deactivated.

Schedule of assessment visits

Assessments at baseline, after the intensive WL phase (6-months), after the entire 9-month WL intervention (9-months) and at study end (18-months) include: the primary outcome of body weight, as well as physical activity energy expenditure, light, moderate and vigorous activity minutes, and sedentary behavior minutes and breaks. The other secondary outcome assessments (RMR, physical function and measures of cardiometabolic risk) will be performed at baseline, after the intensive WL phase (6-months), and at study end (18-months) (See Table). At follow up, Visit 7 and 8 may be combined to help with participant burden and some questionnaires will be administered over the phone to limit the time in the clinic.

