Data analyses: Initial analyses will follow the “intent-to-treat” principle in which data from all randomized participants are analyzed according to their randomized groups. We will document withdrawal and compliance in detail. We will attempt to identify baseline covariates that predict

attrition and compliance, and if such covariates can be identified, the analyses may need to incorporate stratification by these factors to decrease bias. Aim 1 hypothesis will be tested using analysis of covariance (ANCOVA) to compare group differences in 18-mo body weight, adjusted for baseline weight, gender (used to stratify randomization), and treatment arm. Differences in least-squares means and associated 95% confidence intervals will be calculated. Bonferroni adjustment will be used to account for multiple comparisons.

Secondary analyses (Aims 2 & 3)—Hypotheses of Aim 2 secondary outcomes will be tested using ANCOVA with repeated measures, where within subject correlations will be accounted for by using a compound symmetry covariance structure. Differences in least-squares means and associated 95% confidence intervals will be calculated. Group differences in breaks in SB will be tested using a generalized linear model with repeated measures, since a Poisson distribution is a better fit for such count data. Linear regression will be used to examine whether total physical activity energy expenditure and sedentary behavior at 6-months is predictive of less weight regain at 18-months, adjusted for baseline body weight and gender.

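### The Aim 2 regain regression takes activity at month 6, but its hypothesis names activity after the WL phase, which ends at month 9; the regression text also gives no starting visit for regain

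*Combined protocol and SAP*

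**What the plan says.** Under Objectives, Aim 2 sets out to "determine if these factors predict weight regain during the 9-month follow-up phase". Its second hypothesis, stated irrespective of treatment arm, is that greater activity energy expenditure and "fewer minutes of sedentary behavior after the WL phase will be predictive of less weight regain during follow-up".

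The Study Overview describes a "9-month WL intervention (6-mo intensive phase and 3-mo reduced contact phase), followed by a 9-month self-managed follow-up phase". The descriptions of the weight-loss, SitLess and aerobic exercise interventions each use a 9-month WL phase, and the Weight Loss intervention text dates the follow-up phase to months 10-18.

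The Schedule of assessment visits has weight and activity measured at baseline, 6, 9 and 18 months. It ties month 6 to the end of the intensive phase and lists separately the visits "after the entire 9-month WL intervention (9-months) and at study end (18-months".

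The analysis is one sentence under Secondary analyses (Aims 2 & 3): a linear regression asking whether "physical activity energy expenditure and sedentary behavior at 6-months is predictive of less weight regain at 18-months, adjusted for baseline body weight and gender".

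**The concern.** The hypothesis and its analysis use different visits. The hypothesis takes the exposure once the WL phase is over, at month 9. The regression takes it at month 6, while treatment for weight loss continues.

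The protocol changes its contact schedule between these visits. On the weekly weight-loss sessions it says "These group meetings will transition to bimonthly group meetings during months 7-9". In the two EX arms, participants attend "center-based sessions for at least 3 days/week during the first intensive 6-month phase", then "at least one day/week during the second 3-month transition phase (months 7-9". WL+SitLess has no center-based exercise sessions to lose. Month-6 activity is therefore recorded before contact is reduced, and participants' relative activity could change by month 9.

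A smaller point is that the outcome, regain at 18 months, has no starting visit in the regression sentence. Aim 2 implies month 9. Appendix A, for the MRI ancillary study, counts regain from month 6 to month 18. With both windows in one document, the interval for Aim 2 should be written down before data are seen.

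At stake is the only planned test of a named Aim 2 hypothesis. If month-6 activity is an imperfect proxy for month-9 activity, a real association could be understated or missed.

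**Working it through.** The documents give no power, effect size or significance level for this regression, so there is no planned figure to reproduce. The finding rests on the text; the arithmetic only shows how much the choice of visit could matter.

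**1. Timing**

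| Element | Aim 2 and its hypothesis | Regression text |
|---|---|---|
| Activity measured | After the WL phase: month 9 | Month 6 |
| Regain starts | Start of follow-up: month 9 | Not stated |
| Regain ends | End of follow-up: month 18 | Month 18 |

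- The predictor is taken 9 − 6 = 3 months before the WL phase ends.
- Regain from month 9 spans 18 − 9 = 9 months, as Aim 2 says.
- If the Appendix A window were used, regain would span 18 − 6 = 12 months, of which 3/12 = 25% lie inside the WL phase.

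**2. Illustrative loss of power**

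Inputs from the Sample size text and Table 5: 51 completers per group, so N = 3 × 51 = 153.

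Assumptions not in the documents:

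- The test is two-sided at alpha 0.05.
- Each activity predictor has its own model.
- Month-6 activity relates to 9-18-month regain only through month-9 activity.
- The two activity measures have correlation r, given the covariates.

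The model has an intercept, one activity predictor, baseline weight and gender, so residual df = 153 − 4 = 149.

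For a partial correlation ρ, the t statistic has noncentrality ρ/√(1 − ρ²) × √149. Power of 80% needs ρ of about 0.225: 0.225/√(1 − 0.0506) × √149 ≈ 2.82.

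Under these assumptions the month-6 measure has partial correlation r × ρ. Its standardized slope is multiplied by r, and the sample needed for equal power by about 1/r².

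| r | r × 0.225 | Power with month-6 measure | 1/r² |
|---|---|---|---|
| 0.9 | 0.203 | 0.71 | 1.23 |
| 0.8 | 0.180 | 0.60 | 1.56 |
| 0.7 | 0.158 | 0.49 | 2.04 |
| 0.6 | 0.135 | 0.38 | 2.78 |

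A simulation with 8,000 data sets per value of r gave 0.71, 0.60, 0.48 and 0.37. It builds in the same assumptions, so it confirms the arithmetic and not the assumptions.

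**3. Relaxing the strongest assumption**

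Suppose month-6 activity also has a direct effect half the size of month-9 activity's, with the month-9 correlation held at 0.225. If the month-9 coefficient is b, the month-9 correlation is b(1 + 0.5r) and the month-6 correlation is b(r + 0.5). The slope is then multiplied by (r + 0.5)/(1 + 0.5r).

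- r = 0.8: 1.3/1.4 = 0.93, power about 0.74 instead of 0.60.
- r = 0.7: 1.2/1.35 = 0.89, power about 0.70 instead of 0.49.

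The loss shrinks but does not vanish.

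**The case against.** The best case for the plan is that month 6 was chosen deliberately. The protocol labels that visit as the end of the intensive weight-loss phase, and asking whether early activity predicts later regain is a legitimate question. But the plan gives no such rationale, the hypothesis does not say intensive, and it ties regain to a follow-up phase that begins after month 9. The two passages still disagree.

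A second objection is that the fall in supervised sessions does not show a fall in activity. Home-based exercise fills the remaining days, the goal stays at 200 min/week, and daily Fitbit wear continues through month 9. This stands: the text documents a change in contact and supervision, and a change in measured activity is plausible but not documented.

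Third, the power figures depend on an unknown r and on full mediation. This also stands, as step 3 of the working shows. They indicate a possible size and are not evidence of harm.

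Fourth, the starting visit can be inferred from Aim 2, and the month-6 window belongs to a separate ancillary study. That is fair. The second point is a gap in the regression sentence rather than a contradiction, and the 25% figure applies only if that window were borrowed.

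**Conclusion.** The concern holds. The regression uses activity 3 months before the end of the WL phase, whereas its hypothesis uses activity after that phase, and no reading of the protocol's phase definitions reconciles them. The mismatch is established from the text and needs no assumption.

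Its consequence cannot be fixed from the documents. Under full mediation, power of 80% would fall to between 71% (r = 0.9) and 38% (r = 0.6); with a direct month-6 effect the loss would be smaller. The missing starting visit for regain is a lesser point.

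This should be fixed, but its reach is limited to one secondary association. The primary analysis and the sample size do not depend on it.

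**What to change.** In the regression sentence under Secondary analyses (Aims 2 & 3):

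- Name 9-month ActivPAL energy expenditure and 9-month sedentary minutes as the predictors.
- Define regain as 18-month weight minus 9-month weight.
- Keep baseline weight and gender as covariates, and say whether the two activity predictors enter separate models or one.
- Report the 6-month predictors, with the same 9-18-month regain, as a labelled sensitivity analysis.

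If month 6 was intended, the alternative is to reword the Aim 2 hypothesis to match and give the reason, still stating the regain interval.

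As a suggestion only, also report the model with treatment arm included, so that an association irrespective of arm can be separated from a difference between arms.

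The cost is wording. No visit or measurement is added, and with 153 completers the residual df stay at 149 per predictor in separate models (153 − 5 = 148 in a joint model; 149 − 2 = 147 in a separate model with arm). The one real cost is that a participant seen at months 6 and 18 but not at month 9 would drop out of the main model. The documents do not give 9-month retention, so that number is unknown.

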Hypotheses of our Aim 3 secondary outcomes will be tested at the 0.05 significance level using ANCOVA techniques similar to those used for the primary hypothesis. All initial models will be adjusted only for gender and baseline variable value; however, specific factors (e.g., age, race, initial body weight or composition, medication or supplement use, etc.) that may influence the measured responses to the interventions will be evaluated and possibly included in secondary analyses. We expect the treatments to similarly affect responses in men and women and between races. Nevertheless, we will assess whether there is an interaction between gender and/or race and treatment group, and will report this as part of our secondary results. We will also consider conducting analyses adjusted for intervention compliance and process measures (such as average attendance at the exercise sessions, amount of initial weight lost, social cognitive/group process measures, etc.) to examine the extent to which these factors moderate/alter the effect of the intervention on the outcomes.

Human Subjects Protection

Subject Recruitment Methods: We will recruit individuals using community-based recruitment strategies including newspaper ads and mass mailings. We will also advertise in the Aging Center's VITAL newsletter and participate in community outreach events.

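### The optional analyses that adjust arm comparisons for exercise attendance, initial weight lost and social cognitive measures would not test moderation, and their adjusted contrasts would not be randomized effects wherever arms differ on the covariate

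*Combined protocol and SAP*

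**What the plan says.** Under Statistical Analyses, the Aim 1 ANCOVA of 18-month weight is "adjusted for baseline weight, gender (used to stratify randomization), and treatment arm". For the later aims, "All initial models will be adjusted only for gender and baseline variable value". Neither contains anything measured after randomization.

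The same text then adds: "We will also consider conducting analyses adjusted for intervention compliance and process measures". The examples are "average attendance at the exercise sessions, amount of initial weight lost" and measures of social cognition and group process, and the purpose is to examine "the extent to which these factors moderate/alter the effect of the intervention on the outcomes". The text does not say which outcomes or contrasts are meant, and gives no estimand, mediation method or exploratory label. For gender and race it does plan a test of interaction with treatment group; for the process measures it mentions only adjustment.

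Under Study Interventions, "Participants in the WL+EX and WL+EX+SitLess treatment arms will be asked to perform structured aerobic exercise". WL+SitLess is given no exercise sessions.

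**The concern.** Adjusting for a variable and testing whether it moderates an effect are different analyses. Moderation needs an arm-by-factor interaction, and for a clean reading the factor must be fixed before randomization. Attendance, early weight loss and social cognitive scores can all be changed by the assigned arm. Conditioning on them removes whatever part of the effect runs through them. It also compares participants who reached the same value for different reasons, such as motivation, so what remains is not a clean direct effect either.

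The plan itself expects arm differences on two of the three. The Objectives say that in pilot work SitLess improved weight loss during treatment. Aim 3 treats social cognitive measures as outcomes and predicts a larger improvement with WL+EX+SitLess. For body weight, initial loss is also an earlier component of the 18-month outcome. The third, exercise attendance, has no value at all in WL+SitLess, an arm that appears in both the primary and the secondary Aim 1 hypotheses.

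At stake is the reading of mechanism. Without a stated method or label, an adjusted contrast could be reported as showing how or for whom the intervention works.

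**Working it through.** **Inputs from the documents (sample size text and Table 5).** SD 8.2 kg, pre-post correlation 0.87, difference 2.7 kg, two-sided alpha 0.025 per primary comparison, 51 completers per arm. A lower weight with WL+EX+SitLess is written below as -2.7 kg.

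**The plan's own figure first.** ANCOVA residual SD = 8.2 × √(1 - 0.87²) = 4.043 kg. SE of a contrast = 4.043 × √(2/51) = 0.80 kg. Power = Φ(2.7/0.80 - 2.241) = 0.871, against 0.87 in Table 5. The base model is therefore the plan's.

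**Adjusting for initial weight lost.** Adjusted contrast = -2.7 - b × dL. Here dL is the arm difference in initial loss, and b = -r × 4.043/SD_L is the within-arm slope of 18-month weight on initial loss. The documents give neither SD_L (the SD of initial loss) nor r, the within-arm correlation of greater initial loss with lower 18-month weight. I assume SD_L of 3-5 kg and r of 0.6-0.9, so b runs from -0.6 × 4.043/5 = -0.49 to -0.9 × 4.043/3 = -1.21.

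| Share of the 2.7 kg arising early | dL (kg) | Adjusted contrast (kg) |
|---|---|---|
| None | 0 | -2.70 |
| Half | 1.35 | -2.05 to -1.06 |
| All | 2.7 | -1.39 to +0.57 |

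The sign changes only if |b| × dL exceeds 2.7 kg. With all of the effect early, that needs |b| above 1. Of the nine combinations from SD_L 3, 4, 5 and r 0.6, 0.8, 0.9, two meet it (SD_L 3 with r 0.8 or 0.9). As a sensitivity case beyond the table, if the early gain were 1.3 times the final gain, the range would be -1.00 to +1.56 kg.

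Simulated three-arm trials (51 per arm, 1,500 runs per scenario) agree. Without process covariates the contrast is about -2.7 kg, SE 0.80, power 0.85-0.88. With initial loss added (SD_L 4, r 0.8, half early) it is -1.61 kg. With SD_L 3, r 0.8 and all early it is +0.2 kg, with the wrong sign in about 65% of runs.

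**Adjusting for attendance, coded zero in WL+SitLess.** Assume mean attendance of 0.70 and SD 0.20 in the exercise arms; neither figure is in the documents. Let k be the within-arm correlation of attendance with lower 18-month weight. The contrast with WL+SitLess shifts by k × (4.043/0.20) × 0.70 = 14.15k kg:

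- k = 0.1: -2.7 + 1.4 = -1.3 kg
- k = 0.2: -2.7 + 2.8 = +0.1 kg
- k = 0.4: -2.7 + 5.7 = +3.0 kg

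Simulation at k = 0.4 gave +3.2 kg and an SE of 1.62, twice the unadjusted SE. The contrast with WL+EX stayed at -2.7 kg, because attendance was set equal in the two exercise arms.

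**Attendance left missing in WL+SitLess.** The model drops 51 of 3 × 51 = 153 completers, and neither contrast with that arm can be estimated.

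**The case against.** The strongest reply is that the plan commits to none of this. The analyses are only to be considered, after intent-to-treat models that are free of process measures. That stands: a reader might infer that the trial's planned arm comparisons are adjusted for post-randomization variables, and the documents do not support it.

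Second, the plan never claims that the adjusted contrast estimates the randomized effect, and it already plans gender and race interactions. That is true, but the stated purpose is still moderation, and the stated method does not deliver it.

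Third, a shift is not automatic. It is zero if arms do not differ on the covariate or the covariate is unrelated to outcome, and the contrast between the exercise arms is untouched when their attendance is equal. That stands too, although the plan's own rationale predicts arm differences in early loss and social cognitive measures.

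Fourth, attendance is only an example, and the sentence does not say that it would enter a three-arm model. Restricting it to the two exercise arms is compatible with the text. That is fair, and it is a reason to write the restriction down.

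Fifth, initial loss is part of the outcome only for body weight. For fitness, fatigue or cardiometabolic outcomes it is at most a mediator. This is accepted.

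**Conclusion.** The point holds as a minor one about contemplated secondary analyses. Run as described, they would answer neither a moderation question nor, without further assumptions, a mediation question. The primary and initial tests are unaffected.

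For 18-month weight, adjusting for initial loss would move a true -2.7 kg to about -1.1 to -2.1 kg if half the effect is early, and to -1.4 to +0.6 kg if all of it is. These ranges rest on the assumed SD and correlation of initial loss. Not all of the shift is error, since some is the part of the effect that runs through early loss; the model cannot separate the two.

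A reader might infer that adjustment for initial loss would turn benefit into apparent harm. The documents do not support that as the expected result. It needs an early difference about as large as the final one, or larger, together with a steep slope, and the trial is aimed at maintenance of lost weight.

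The attendance problem is structural. In a three-arm model, either coding fails for the WL+SitLess contrasts. Its size when coded zero (about -1.3 to +3 kg for k of 0.1 to 0.4) depends on the assumed attendance figures.

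**What to change.** Replace the sentence on compliance and process measures with text that:

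- tests moderation only through arm-by-factor interactions with baseline variables;
- analyses exercise attendance only as dose-response within WL+EX and WL+EX+SitLess, or uses an adherence measure defined in all three arms, labelled exploratory and non-causal;
- treats initial weight loss and social cognitive measures as mediators, with the assumptions stated and a sensitivity analysis for unmeasured confounding;
- reports the intent-to-treat estimate beside every process result.

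An instrumental-variable estimate with randomization as the instrument may look like a natural way to handle attendance, but I would not recommend it here. The exercise arms also have home-based exercise and activity feedback from the Fitbit, so assignment can affect weight by routes other than session attendance.

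The cost is a few sentences in the plan, a little more analysis work, and process results that support only weaker claims. Sample size, data collection and the primary analysis do not change.
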